4.4 POST-TRIAL ACCESS TO MHAA4549A

As this is single dose administration, Genentech does not intend to provide MHAA4549A to patients after the conclusion of the study or any earlier withdrawal. Patients may or may not be eligible for any potential subsequent trials of MHAA4549A under a separate protocol.

4.5 CONCOMITANT THERAPY AND FOOD

4.5.1 Permitted Therapy

Concomitant medication includes any medication (e.g., prescription drugs, over-the-counter drugs, herbal or homeopathic remedies, nutritional supplements) used by a patient from 30 days prior to screening to the study completion/discontinuation visit. All concomitant medications should be reported to the investigator and recorded on the Concomitant Medications eCRF. For any NAIs (e.g., oseltamivir, peramivir, zanamivir, laninimavir) that have been taken prior to study drug therapy, the number of doses and duration of therapy must be recorded.

Patients who use oral contraceptives, hormone-replacement therapy, or other maintenance therapy should continue their use.

All therapies required for management of the patient's acute illness are permitted except for those listed below in [Section 4.5.2](#).

4.5.2 Prohibited Therapy

Use of the following therapies is prohibited during the study and for at least 7 days prior to study treatment, unless otherwise specified below: probenecid, amantadine, or rimantidine

Use of other NAIs, including but not limited to oral oseltamivir, inhaled zanamivir, oral ribavirin, laninimivir, and peramivir, are prohibited during the study, but allowed up to 3 days (6 doses) prior to study treatment as outlined in the exclusion criteria. If oseltamivir resistance is highly suspected or identified during treatment then, following discussion with the sponsor medical representative, an alternative NAI to oseltamivir may be used.

4.5.3 Prohibited Food

There are no prohibited foods for this study.

4.6 STUDY ASSESSMENTS

Please see [Appendix 1a](#) and [Appendix 1b](#) for the schedule of assessments performed during the study.

4.6.1 Informed Consent Forms and Screening Log

Written informed consent for participation in the study must be obtained before performing any study-specific screening tests or evaluations. Informed consent by authorized representatives may be obtained only if allowed by and in accordance with local regulations and Independent Review Board (IRB)/Independent Ethics Committee (IEC) policies and procedures. Informed Consent Forms (ICF) for enrolled patients and for patients who are not subsequently enrolled will be maintained at the study site.

All screening evaluations must be completed and reviewed to confirm that patients meet all eligibility criteria before randomization. The investigator will maintain a screening log to record details of all patients screened and to confirm eligibility or record reasons for screening failure, as applicable.

4.6.2 Diagnostic Testing for Enrollment

All hospitalized patients with severe influenza A will be assessed for disease confirmation and enrollment into the study. A Sponsor-supplied rapid influenza test is required for the diagnosis of influenza A infection and uses a nasopharyngeal swab. When the Sponsor-supplied rapid influenza test is negative, the study inclusion criteria can be satisfied with a positive local molecular test (PCR) if the result is within the 48-hour screening window. Patients may be enrolled based on a positive local molecular test (PCR) result within the 48-hour screening window, but the rapid influenza test must still be conducted prior to randomization. Other tests may not be used for enrollment in the study unless the Sponsor has reviewed and approved the use of the diagnostic.

4.6.3 Medical History and Demographic Data

Medical history includes clinically significant diseases and procedures, including chronic respiratory disease, infections, surgeries, cancer history (including prior cancer therapies and procedures), reproductive status, smoking history, use of alcohol and drugs of abuse, and all medications (e.g., prescription drugs, over-the-counter drugs, herbal or homeopathic remedies, nutritional supplements) used by the patient within 30 days prior to the screening visit. A careful assessment of the patient's baseline SpO₂ should be made especially if the patient has a history of severe chronic lung disease.

Demographic data will include age, sex, and self-reported race/ethnicity.

4.6.4 Priority of Assessments

When events warrant, or in the opinion of the investigator, safety issues become paramount, safety assessments will always have priority over all other measurements and procedures. Under routine circumstances, however, PK, nasal virological, and biomarker serum/plasma samples have priority over other measurements. The timing and number of safety measurements may be modified based on clinical evaluations.

4.6.5 Physical Examinations

A complete physical examination should include an evaluation of the head, eyes, ears, nose, and throat, and the cardiovascular, dermatological, musculoskeletal, respiratory, gastrointestinal, genitourinary, and neurological systems. Any abnormality identified at baseline should be recorded on the General Medical History and Baseline Conditions eCRF.

At protocol designated visits (or as clinically indicated), limited, symptom-directed physical examinations should be performed which includes, at a minimum, evaluation of general appearance, dermatological examination of the injection sites, evaluations directed by patient-reported symptoms, and any other evaluations that the investigator deems clinically relevant. Changes from any prior examination should be recorded. New or worsened abnormalities should be recorded as AEs, if appropriate, on the AE eCRF.

4.6.6 Vital Signs

Vital signs will include measurements of resting SpO₂ (see [Section 4.6.7](#) for measurement), respiratory rate, pulse rate, temperature, and systolic and diastolic blood pressures after the patient has been in a seated or supine position for at least 10 minutes. Patients in intensive care may have vital signs assessed following local procedures, but those procedures should be captured in the eCRF in accordance with the eCRF instructions.

4.6.7 Oxygen Saturation Measurements

To ensure that the respiratory status is well recorded, the following daily measurements will be performed. Unless clinically contraindicated, all patients will have their SpO₂ and corresponding respiratory assessments recorded daily in the morning between 6 am – 12 pm local time. Patients on low-flow O₂ will have a daily trial of their SpO₂ while on and off the supplementation, as outlined in [Appendix 2](#), and both values will be recorded.

If the patient is on oxygen supplementation, SpO₂ measured by pulse oximetry and the corresponding respiratory assessments (e.g. FiO₂, flow rate) will be recorded. If the patient is on PPV, partial pressure of O₂ (PaO₂) and the corresponding respiratory assessments (e.g. FiO₂, ventilator mode, ventilator respiratory rate, positive end-expiratory pressure) will be recorded.

4.6.8 Laboratory, Biomarker, and Other Biological Samples

Samples for the laboratory tests listed in [Table 3](#) and [Table 4](#) will be sent to the study site's local laboratory for analysis at screening and during the study, respectively.

Table 3 Laboratory Tests at Screening

Hematology:	Clinical Chemistry:
Hemoglobin	Thyroid stimulating hormone (optional)
Hematocrit	
Erythrocyte count (RBC)	Serology:
Leukocytes (WBC)	HIV Serology
Neutrophils, segmented & bands	
Lymphocytes	Misc:
Monocytes	Pregnancy Test (urine or serum; women of child-bearing potential)
Eosinophils	
Basophils	
Platelets	

Note: Investigators must document their review of each laboratory report by signing (or initialing) and dating each report.

Table 4 Laboratory Tests During the Study

Hematology:	Clinical Chemistry (Blood):
Hemoglobin	Sodium
Hematocrit	Potassium
Erythrocyte count (RBC)	Bicarbonate
Leukocytes (WBC)	Chloride
Neutrophils, segmented & bands	Calcium
Lymphocytes	Phosphorus
Monocytes	Magnesium
Eosinophils	Glucose
Basophils	Urea nitrogen (BUN) or urea
Platelets	Creatinine
Erythrocyte Sedimentation Rate (ESR) (optional)	Total cholesterol
	Total protein
Coagulation:	Albumin
Activated partial thromboplastin time (APTT)	Total bilirubin
Prothrombin time (PT)	Alkaline phosphatase
International Normalized Ratio (INR)	Aspartate aminotransferase (AST)
	Alanine aminotransferase (ALT)
Urinalysis:	Amylase
pH	Gamma-glutamyl transpeptidase (GGT) (if clinically indicated)
Specific gravity	C-reactive protein (CRP) (optional)
Glucose	
Protein	
Ketones	Misc:
Blood	Pregnancy Test (if clinically indicated)
Bilirubin	
Nitrite	
Leukocyte esterase	
Microscopic examination (if clinically indicated)	

Note: Investigators must document their review of each laboratory report by signing (or initialing) and dating each report.

The following samples will be sent to the Sponsor or a designee for PK or ATA analysis:

- [REDACTED]
- [REDACTED]

- [REDACTED]
- [REDACTED]
- [REDACTED]
- [REDACTED]

For sampling procedures, storage conditions, and shipment instructions, see the laboratory manual.

4.6.9 Electrocardiograms

Single ECG recordings will be obtained at specified timepoints, as outlined in the schedule of assessments (see [Appendix 1a](#) and [Appendix 1b](#)), and may be obtained at unscheduled timepoints as indicated.

All ECG recordings must be performed using a standard high-quality, high-fidelity digital electrocardiograph machine equipped with computer-based interval measurements. Lead placement should be as consistent as possible. ECG recordings must be performed after the patient has been resting in a supine position for at least 10 minutes. All ECGs are to be obtained prior to other procedures scheduled at that same time (e.g., vital sign measurements, blood draws) and should not be obtained within 3 hours after any meal. Circumstances that may induce changes in heart rate, including environmental distractions (e.g., television, radio, conversation) should be avoided during the pre-ECG resting period and during ECG recording.

For safety monitoring purposes, the investigator must review, sign, and date all ECG tracings. Paper copies of ECG tracings will be kept as part of the patient's permanent study file at the site. The following should be recorded in the appropriate eCRF: heart rate, RR interval, QRS interval, PR duration, uncorrected QT interval, and QTcF based on the machine readings of the individual ECG tracings. Any morphologic waveform changes or other ECG abnormalities must be documented on the eCRF. If considered appropriate by the Sponsor, ECGs may be analyzed retrospectively at a central laboratory.

If at a particular postdose timepoint the mean QTcF is > 500 ms and/or > 60 ms longer than the baseline value, another ECG must be recorded, ideally within the next 5 minutes, and ECG monitoring should continue until QT interval corrected using Fridericia's formula (QTcF) has stabilized on two successive ECGs. The Medical Monitor should be notified. If QTcF is not available, QTcB may be recorded. Standard of care treatment may be instituted per the discretion of the investigator. If a PK sample

is not scheduled for that timepoint, an unscheduled PK sample should be obtained. A decision on study drug discontinuation should be made, as described in [Section 4.9.2](#). The investigator should also evaluate the patient for potential concurrent risk factors (e.g., electrolyte abnormalities, medications known to prolong the QT interval, severe bradycardia).

4.6.10 [REDACTED]

[REDACTED]

[REDACTED]

[REDACTED]

[REDACTED]

[REDACTED]

[REDACTED]

[REDACTED]

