HA	Hemagglutinin
HAI	Hemagglutinin inhibition
HAP	Hospital Acquired Pneumonia
HIPAA	Health Insurance Portability and Accountability Act
HIV	Human Immunodeficiency Virus
HR	Heart rate
█	█
ICH	International Conference on Harmonisation
ICU	Intensive Care Unit
IEC	Independent Ethics Committee

Abbreviation	Definition
IMC	Internal Monitoring Committee
IMP	Investigational medicinal product
IND	Investigational New Drug (application)
IRB	Institutional Review Board
IRR	Infusion-related reactions
IV	Intravenous
LFTs	Liver function tests
mAB	Monoclonal antibody
NAI	Neuraminidase inhibitor
NP	Nasopharyngeal
PaO ₂	Partial pressure of arterial oxygen
PCR	Polymerase Chain Reaction
PD	Pharmacodynamic
PK	Pharmacokinetic
PPV	Positive pressure ventilation
qPCR	Quantitative Polymerase Chain Reaction
QTcB	QT interval corrected using Bazett's formula
QTcF	QT interval corrected using Fridericia's formula
RBC	Red blood cell
RNA	Ribonucleic acid
SAE	Serious adverse event
SAP	Statistical analysis plan
SAP	Statistical analysis plan
SBP	Systolic blood pressure
SOC	Scientific Oversight Committee
SpO ₂	Oxygen saturation by pulse oximetry
SUSAR	Suspected unexpected serious adverse reactions
ULN	Upper limit of normal
VAP	Ventilation Acquired Pneumonia

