6.3 SUMMARIES OF TREATMENT GROUP COMPARABILITY

Demographic and baseline characteristics of the patient will be summarized for all randomized patients by treatment group by use of descriptive statistics. Baseline is defined as the last available value prior to study drug administration.

During the study; patient disposition, concurrent treatment, and compliance with study treatment and visits will be summarized on the safety analysis population using descriptive statistics.

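### Section 4.6.9 sets its ECG alert on QTcF but lets sites record QTcB instead, with no rule for one formula per patient; at raised heart rates the alert can miss a true rise above 60 ms or fire on a small one

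*Combined protocol and SAP*

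**What the plan says.** Section 4.6.9 (Electrocardiograms, Version 3) asks sites to enter on the eCRF "heart rate, RR interval, QRS interval, PR duration, uncorrected QT interval, and QTcF based on the machine readings of the individual ECG tracings". ECGs are single recordings: "Single ECG recordings will be obtained at specified timepoints".

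The alert applies when "the mean QTcF is > 500 ms and/or > 60 ms longer than the baseline value". It leads to a repeat ECG, continued monitoring until QTcF has settled, notice to the Medical Monitor, a PK sample if none is due at that time, and a decision about study drug.

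The same paragraph then says "If QTcF is not available, QTcB may be recorded". The List of Abbreviations defines QTcB as the "QT interval corrected using Bazett's formula". The sentence came in with Version 2 and is repeated in Version 3; the first protocol version does not have it.

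Section 4.6.9 does not define the baseline for the alert. Section 6.3 says "Baseline is defined as the last available value prior to study drug administration". Appendix 1a puts the first ECG on Day 1, with Day 1 assessments before dosing unless otherwise indicated. Later ECGs fall on Day 5, Day 14, discharge, Day 30 and Day 60.

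**The concern.** The two corrections agree only at 60 bpm. Above that, Bazett gives the larger value, and the gap widens with heart rate. The baseline ECG is taken within 48 hours of admission for severe influenza, and later ones are taken as patients recover. The protocol itself counts a heart rate below 100 as a recovery criterion (Section 3.3.3), so it expects the rate to fall between baseline and follow-up in at least some patients.

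The text allows two problems:

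- One patient's baseline and post-dose values may come from different formulas, so the change mixes two scales.
- If QTcB is used at both times, a falling heart rate lowers the post-dose value relative to baseline and offsets part of any true prolongation.

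At stake is an alert that should prompt a repeat tracing and a call to the Medical Monitor. ECG parameters are named in the safety objective (Section 2.1). QTc values are machine readings at a planned 170 or so centers. Central reading is optional and retrospective, so it cannot correct an alert in real time.

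**Working it through.** **Inputs.** The alert limits and the fallback come from Section 4.6.9. The documents give no baseline heart rates, no QTc values and no frequency with which QTcF is unavailable. Heart rate and true QTcF are therefore assumptions, shown over a range. For orientation, Appendix 8 grades tachycardia as 101–115 bpm (Grade 1) and 116–130 bpm (Grade 2). The plan states no QTcB–QTcF difference, so there is no figure of its own to reproduce.

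**Formulas**, with RR = 60/heart rate in seconds:

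- QTcF = QT / RR^(1/3)
- QTcB = QT / RR^(1/2)
- hence QTcB = QTcF × RR^(-1/6)

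**Shift, QTcB minus QTcF**

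| Heart rate (bpm) | RR (s) | RR^(-1/6) | QTcF 400 ms | QTcF 420 ms |
|---|---|---|---|---|
| 80 | 0.750 | 1.049 | 19.6 | 20.6 |
| 90 | 0.667 | 1.070 | 28.0 | 29.4 |
| 100 | 0.600 | 1.089 | 35.5 | 37.3 |
| 110 | 0.545 | 1.106 | 42.5 | 44.6 |
| 120 | 0.500 | 1.122 | 49.0 | 51.4 |

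**Missed alert, mixed formulas.** True QTcF is 420 ms at baseline, recorded as QTcB at 110 bpm: 420 × 1.1063 = 464.6. Post-dose QTcF is 490, a true rise of 70 ms, so an alert is due. The recorded change is 490 − 464.6 = +25 ms, and 490 is below 500. Neither limit fires.

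**Missed alert, QTcB both times.** True QTcF is 400 ms at 110 bpm: 400 × 1.1063 = 442.5. Post-dose true QTcF is 480 ms at 75 bpm, where RR^(-1/6) = 0.8^(-1/6) = 1.0379: 480 × 1.0379 = 498.2. The true rise is 80 ms. The recorded change is 498.2 − 442.5 = +56 ms, and 498 is below 500. Neither limit fires.

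**False alert.** Baseline QTcF is 420 ms, followed by QTcB at 110 bpm. The change limit is crossed when QTcF × 1.1063 exceeds 480, that is, when QTcF exceeds 480 / 1.1063 = 433.9. A true rise of about 14 ms is enough. On the absolute limit, QTcB passes 500 at 110 bpm once true QTcF passes 500 / 1.1063 = 452 ms.

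**How far the 500 ms limit contains the misses.**

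- Mixed formulas, as in the first case: post-dose QTcF above 500 fires regardless, so the missed range is true rises above 60 and up to 500 − 420 = 80 ms. With a 400 ms baseline it is up to 100 ms.
- QTcB both times, as in the second case: QTcB passes 500 at QTcF 500 / 1.0379 = 481.7, so the missed range is above 60 and up to about 82 ms. From a 420 ms baseline it closes at about 62 ms.

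**Where the problem nearly vanishes.** With QTcB both times and the rate constant at 110 bpm, the change limit fires at a true rise of 60 / 1.1063 = 54 ms, close to the intended 60.

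**The case against.** The strongest reply is that the exposure is narrow and the data are not lost. The fallback applies only where the machine gives no QTcF, and no document says how often that is. ECGs follow 10 minutes of supine rest, so heart rates may be lower than assumed. QT, RR and heart rate are to be entered, investigators review every tracing, and paper copies are kept. Any later analysis can therefore use Fridericia throughout. This stands, and it confines the harm to the alert as it operates during the study.

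Several stronger readings are tempting, but the documents do not support them:

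- A reader might infer that the formula shift alone sets off a false alert. At 110 bpm and QTcF 420 ms it adds 45 ms, which is below the limit; a further rise of about 14 ms is needed.
- A reader might infer that a true rise of exactly 60 ms is missed. The limit is above 60 ms, so that rise would not fire under QTcF either.
- A reader might infer that by-arm summaries of QTc change will mix scales. Section 6.5 lists ECGs as a safety parameter but specifies change from baseline only for vital signs.
- A reader might infer that a missed alert loses a drug concentration. Appendices 1a and 1b already schedule serum PK at every scheduled post-dose ECG visit.
- A reader might take 40 to 50 ms as the general shift. It needs roughly 105 to 120 bpm; at 80 to 90 bpm the shift is 20 to 29 ms.

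It is also fair to say that QT and RR are fields sites should complete, which does not guarantee that they always will.

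**Conclusion.** The point holds, limited to the real-time alert. Section 4.6.9 permits a different correction without saying how to judge it against limits written for QTcF, and does not require the same correction at baseline and post-dose. Under plausible but assumed values, true rises of 70 and 80 ms escape both limits, and a true rise of about 14 ms can fire the alert.

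The result rests on raised heart rates at the ECGs where QTcB is used. It also needs either mixed formulas within a patient or a heart rate that changes between ECGs. With QTcB at both times and a steady rate there is almost no artefact on the change limit, although the 500 ms limit is still reached at a lower true QTcF.

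The text examined is Version 3 (VHP Only), with the same sentence in Version 2. The body of Version 5 (Global) was not available, so whether the sentence survives there must be checked. Because the remedy costs almost nothing, the change should be made if it does.

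**What to change.** Replace the fallback sentence with: *If the machine does not report QTcF, it will be derived as QT/RR^(1/3) (RR in seconds) from the recorded QT and RR.* Have the eCRF calculate QTcF the same way for every tracing, so that baseline and post-dose values share one formula. The derived value is then the one compared with the alert limits.

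For example, QT 330 ms at 110 bpm gives QTcF 404 ms, against QTcB 447 ms. With one formula at both times, the difference between corrections drops out at every heart rate and the alert keeps its stated meaning.

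The protocol's thresholds and the actions that follow an alert stay unchanged. The cost is one sentence and one derived field, with no new ECGs and no new data items. The derivation needs both QT and RR, so an eCRF query for a missing value in either field would be a sensible companion.

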4.7 APACHE AND SOFA SCORES

Acute Physiology and Chronic Health Evaluation (APACHE) and Sequential Organ Failure Assessment (SOFA) scores are for patients that are admitted into the ICU. These assessments are not required for study conduct or entry but should be collected if available. The initial scores for APACHE and SOFA should be taken within 24 hours of entry into the ICU and at specified time points as seen in [Appendix 1a](#).

For the calculation of the initial APACHE and SOFA scores, the worst values in the first 24 hours of ICU admission should be used. SOFA scores are only for patients admitted into the ICU that have available data for calculation (i.e., partial pressure of arterial oxygen/fraction of inspired oxygen [$\text{PaO}_2/\text{FiO}_2$] in mmHg). See [Appendix 7](#) for SOFA score calculation.

4.8 OSELTAMIVIR MEDICATION DIARY

Patients who are discharged from the hospital with oseltamivir will be required to complete a medication diary and return the medication diary, empty (used) oseltamivir packets, and unused oseltamivir capsules to the study site at the next follow up visit.

Patients will record the date and time when each oseltamivir capsule is administered.

4.9 PATIENT, TREATMENT, STUDY, AND SITE DISCONTINUATION

4.9.1 Patient Discontinuation

Patients have the right to voluntarily withdraw from the study at any time for any reason. In addition, the investigator has the right to withdraw a patient from the study at any time. Reasons for withdrawal from the study may include, but are not limited to, the following:

- Patient withdrawal of consent at any time
- Any medical condition that the investigator or Sponsor determines may jeopardize the patient's safety if he or she continues in the study
- Investigator or Sponsor determines it is in the best interest of the patient

Every effort should be made to obtain information on patients who withdraw from the study. The primary reason for withdrawal from the study should be documented on the appropriate eCRF. However, patients will not be followed for any reason after consent has been withdrawn. Patients who withdraw from the study will not be replaced.

